
## **Screening and Management Guidelines**

Between the 1940s and 2002, women in the U.S. were advised to have cytology screening for cervical cancer performed annually at the time of their well woman visit. Although initially this results in a rapid decline in cervical cancers, little to no change has occurred in most population over the past decade. As reviewed above, studies now show that overscreening may result in overtreatment with excisional therapy which has negative consequences such as premature delivery. Over the past decade, national guidelines have changed substantially to avoid negative outcomes, such that routine screening is started later in life, completed earlier, and performed at greater intervals. In addition, it is advised to observe and follow cytologic and histologic abnormalities in young women rather than perform invasive procedures.

Recently there were several updates to both cervical cancer screening guidelines and management of abnormal cytology and histology. The American Cancer Society (ACS), American Society for Colposcopy and Cervical Pathology and American Society for Clinical Pathology sponsored a systematic evidence review of the ACS guidelines regarding screening for early detection of cervical precancerous lesions and cancer. In parallel, the US Preventive Task Force also reviewed and updated their guidelines. Based on evidence that HPV is extremely common in young women and cancer is extremely rare under the age of 21, it is now recommended that cervical cancer screening not begin until the age of 21 years. It was emphasized that overscreening and overtreatment in this group represents a net harm over underscreening. For women aged 21-29 years, it is recommended that women are screened with cytology along every 3 years and that HPV testing not be used to screen women in this age group, either as a stand-alone or HPV co-test. These guidelines were derived mostly from modeling studies. It was noted that annual screening resulted in twice the number of colposcopies compared with screening every 3 years.

In addition, the 2006 consensus guidelines for management of abnormal cytology and histology were updated. For women under 26 years of age with abnormal cytology and histology, observation with cytology and colposcopy is recommended over invasive treatments such as LEEP and cryotherapy. More specifically, for young women with ASCUS and LSIL, it is recommended to repeat cytology annually and refer to colposcopy only if persistent at 2 years or if HSIL develops. Recommendations continue from the 2006 guidelines that young women with HSIL (CIN 2,3), defined as those interested in fertility, be followed by colposcopy and cytology rather than immediately referred for therapy.

Adherence to these screening and management guidelines has been disappointingly low, although the adherence to other national guidelines in general is low. Dissemination and implementation of these guidelines can be a challenge in the US--many women equate health care with annual Pap smears and continue to demand these examinations. In addition, many physicians may have financial incentives to over screen and treat or are not aware of current guidelines.

This research will be expected to influence adherence to guidelines and lead to improved patient health and well-being as this study would show interventions that are capable of lowering the number of unnecessary colposcopic examinations, cervical biopsies and excisional therapies. All of these procedures have been shown to have negative effects including psychological distress

and premature delivery. Numerous providers and stakeholders have underscored the need to avoid these unnecessary procedures.

There has been little done regarding physician based interventions regarding cervical cancer screening. In general, message based interventions (i.e., messages on laboratory reports), payment denials, and electronic medical record messages have all been examined with mixed results. Newer technologies have not been evaluated extensively in any setting. These include offering free applications (APPs) for mobile phones, which would give easy access to guidelines. In addition, no mobile application intervention for patient decision-making has been applied for cervical cancer screening.

The aims of this study will specifically examine different strategies to increase physician and patient adherence to guidelines with the ultimate aim of obtaining better health and well-being for the woman. To date, no data is available on patient-centered interventions to assist the patient in understanding the guidelines and making informed decision on treatment options. It is important to have a team of experienced researchers, educators, and community stakeholders along with patient input to develop patient centered models. In addition, although mobile applications are becoming more common, there are no studies that have evaluated their success in increasing provider adherence to guidelines.

We also have the unique opportunity to work with the California Office of Family Planning: Family PACT program which serves underinsured women to obtain several preventive care services including cervical cancer screening. This innovative study will take advantage of the Family PACT claims database, which would give us the opportunity to examine reimbursement requests before and after intervention to assess the efficacy of the interventions. This type of outcome data avoids several biases associated with measuring efficacy of interventions.

The results from this research would influence current practice, which would lead to the decrease in unnecessary cervical procedures, and in turn would result in less premature birth and decreased distress caused by these procedures. Our relationship with all of our stakeholders would result in rapid dissemination of the results within Latina communities with the assistance of Latina Contra Cancer, national communities of patients with the assistance of National Cervical Cancer Coalition and our organizational stakeholders, American Society for Colposcopy and Cervical Pathology and American Congress of Obstetrics and Gynecology which both have large member associations and numerous opportunities through their organizations for dissemination.

### **Impact on Health Care Performance**

The development of guidelines are centered toward reviewing the most recent literature so that evidence-based decisions can guide development of guidelines that are based on our best understanding of benefit and harm with each strategy and outcome. Several standards have now been assigned to the review of the literature including a systematic review and weighing of the evidence. The most recent evidence suggested that overscreening women results in more harm than benefit and over treatment is not only costly but has negative effects including psychological distress and premature birth (reviewed above). Modeling studies all showed that these new guidelines are likely to be quite cost-efficient. Data analysis that was performed for the USPTF decision for screening young women every 3 years showed that there were less

colposcopies and less cervical cancer cases for screening every 3 years with cytology and HPV testing starting at 30 than screening every 3 years with cytology alone for all ages. The age at which HPV testing begins to play an important role is 30 years of age when most HPV infections when detected reflect already persistent infections. Until then, most infections are thought to be more recently acquired or have not had adequate change to spontaneously regress. Therefore, cytology alone is best used under 30 years of age. These data support that non-adherence to the guidelines is likely to result in inefficient patient care. As discussed above, there is good evidence that many providers do not adhere to the new guidelines including age of first cytology, screening intervals and overtreatment specifically in young women. Therefore, interventions to decrease overscreening and overtreatment according to the current guidelines will increase the efficiency of patient care and we believe it will also improve the overall quality and experience of their care. We also believe that the patient centered approach will be most efficient since it offers an opportunity for teaching which would then in turn decrease time required of the physician. Patient-centered approach is to educate the patient so that she is armed with critical information to understand the guidelines, ask more focused questions of the provider and ultimately to assist the patient in making informed decisions. The guidelines themselves are very complicated and it is not expected that the patient should be able to maneuver through the guidelines, however, simple messages can be understood by patients who then can assist them to feel comfortable with the new guidelines, and in the case of treatment options, make a decision that they are also more comfortable with making. However, it is likely that a successful intervention will be required for both patients and providers as discussed above.

We believe this project would increase the efficiency of patient care with less unnecessary cytology specimens, less unnecessary referral to colposcopy and biopsy and most important less invasive treatment for CIN in young women that in turn would result in less premature births.

### **Relevance to Patients**

Although referral to colposcopy may seem benign, studies have shown that many women are negatively affected by a diagnosis of an abnormal Pap test or HPV tests including feelings of shame, anxiety, fear, and emotional distress. Relationships are often negatively affected as well when trying to explain the sexually transmitted nature of HPV. Referral to colposcopy also affects work and school activities. Colposcopy and biopsy itself is associated with psychological distress, anxiety and fear. Most women find biopsy uncomfortable and excisional therapies often quite painful. On the other hand, the fear of developing cervical cancer is overwhelming to many women and these women are comforted by having annual examinations that include cervical cancer screening. Cervical cancer screening is always a balance between harm and benefit and this balance is age related. Some younger women may think that since they have received the HPV vaccine that no screening is required. However, since the vaccine only covers 2 of the 15 high-risk types, screening in this population also remains essential and this message must be conveyed.

This proposed research is focused on developing tools that will decrease anxiety and fears about HPV, undo myths and enhance women's participation in obtaining regular health care including appropriate cervical cancer intervals.

## **STUDY DESIGN**

### **Overview**

This is a clustered randomized trial with individual clinics serving as the clusters. Clinics from the California Family PACT provider network who serve at least 200 female clients per year <30 years of age will be randomized to one of 2 intervention arms: 1) physician based approach (APP), and 2) APP-based intervention plus patient-centered approach (PCA). We will reach out to eligible sites to identify which sites are willing to participate. Of these, we will randomize 14 clinics to one of the two intervention arms. These groups will be compared to a comparison group (those not randomized). Since Family PACT data is available for all sites, randomization is not necessary for the comparative groups. However, attention to size, cultural make-up and public versus private information will be accounted for in identifying 7 sites for comparison. Seven sites in each arm/group will result in an average of 2800-3500 women per arm/group—total of 8400-10500 women.

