## **Selection of Participants**

### *Inclusion Criteria*

#### Intervention arms:

We will identify Family PACT providers who meet the following inclusion criteria:

- Is located in one of the ten Southern California study counties
- Clinical care visits occurred to at least 200 women aged 21-29 years in FY 11/12
- Has a calculated average cytology interval of < 30 months (based on last 3 years)
- Cytology is sent to Quest laboratories

For comparison, we will select from the following:

- Is located in one of the ten Southern California study counties
- Clinical care visit occurred to at least 200 women aged 21-29 years in FY 11/12
- Has a calculated average cytology interval of < 30 months (based on last 3 years)
- Cytology is sent to Quest laboratories

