## **Study Implementation Procedures**

### *Study Enrollment Procedures*

#### Contacting sites:

A letter will be sent to all clinic administrators of eligible sites explaining the study. A follow-up phone call will occur one week later. We will explain the study over the phone and those interested and agree to participate will be identified as clinics eligible to randomize to an intervention arm. If more than 14 sites agree to participate, we will let the sites know that they may not be asked to participate. If more than 14 sites agree, the 14 sites will be chosen based on identifying a balance of private and public clinics so that the average number of women aged 21-29 years is 500, and a relative geographic distribution among the 10 counties and that both English and Spanish languages are well represented according to the county's proportion of Hispanics.

Of those eligible for the comparison sites, we will identify sites using the eligibility criteria, and randomly identify 7 sites but with matching for private and public clinics and relative size of

practice which may range from 200 to over 1000 clients. There will be no contact with these sites since the outcomes data will be monitored from the Family PACT claims database.

Randomization:

Block randomization of clinics to one of the two arms will be performed by the biostatistical group at UCLA.

Site set up:

[name] and the PC will visit all 14 identified clinics sites to meet with staff, identify a key contact person for the site, discuss flow issues, and discuss the protocol.

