### **Sample Size Estimates and Power Calculations**

The database for FY 2010/11 shows that 386 clinics fit the criteria with 89 sites available for arms 1-2 and 297 available for the comparison group. The mean number of female clients aged 21-29 years seen at the eligible clinics was 560 and the mean number of cytology specimens, colposcopic examinations and LEEP/cryoprocures for this age group was 297, 40, and 4, respectively. In 2012, the mean cytology interval was 19 months. Very few clinics had an interval >30 months. There were no differences for any of the above variables between those

sites eligible for intervention and those for comparison. These numbers have not changed significantly in the past 2 years and will be updated for the baseline assessment.

After enrolling 7 sites into each arm, we estimate that we would have approximately 2800-3500 women aged 21-29 years in each arm. For each arm, baseline cytology rate in this age group would be approximately 50%, rate of colposcopy procedures for those who had cytology would be 13%, and rate of LEEP/cryotherapy procedures for those referred to colposcopy would be 10%.

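### The primary contrasts compare volunteer clinics with non-randomised clinics, so the design label and conclusions claim more than the allocation supports; randomise three ways if 21 sites agree, otherwise report these contrasts as non-randomised

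*Combined protocol and SAP*

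**What the plan says.** The Overview under Study Design gives the label: "This is a clustered randomized trial with individual clinics serving as the clusters". Eligible sites are approached to find those willing to take part, and then: "Of these, we will randomize 14 clinics to one of the two intervention arms". The comparison group stands outside this step: "These groups will be compared to a comparison group (those not randomized"). The reason given is: "Since Family PACT data is available for all sites, randomization is not necessary for the comparative groups".

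Study Enrollment Procedures says how clinics enter the intervention arms. After a letter and a telephone call, "those interested and agree to participate will be identified as clinics eligible to randomize to an intervention arm". The same section foresees a surplus: "If more than 14 sites agree to participate, we will let the sites know that they may not be asked to participate". Comparison sites are drawn at random from sites that meet the criteria but are not participating (Study Population). They are matched on sector and practice size and are not contacted. The Overview adds cultural make-up as a factor to consider.

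The primary outcome (Data Analyses) is the within-clinic change in cytology testing rate, intervention against comparison. The sample size section bases its calculation on each intervention arm against control. It says the study is not powered for APP against APP+PCA, although it claims at least 70% power for a 15-point difference at the 5% level.

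On the pools, the sample size section reports: "386 clinics fit the criteria with 89 sites available for arms 1-2 and 297 available for the comparison group". It adds that the two sets did not differ on client volume, procedure counts or cytology interval.

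**The concern.** A clinic that agrees to join a project on reducing overscreening may already be changing its practice, or be readier to change, than a clinic that was never asked. If so, testing in the volunteer clinics could fall faster than in the comparison clinics even if the app and tablet did nothing. The analysis would count that gap as an intervention effect.

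The stated reason for not randomising the comparison group does not meet this. Claims data for every site solve the measurement of outcomes. They do not make the clinics that receive the intervention exchangeable with those that do not.

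At stake is the interpretation of both primary tests. Under the label of a cluster randomised trial, readers will take the results against comparison as protected by randomisation. Only the contrast declared underpowered has that protection.

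**Working it through.** **1. Which contrasts are randomised.**

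| Contrast | Clinics | Allocation | Role in the plan |
|---|---|---|---|
| APP vs comparison | 7 vs 7 | Not randomised | Primary, basis of sample size |
| APP+PCA vs comparison | 7 vs 7 | Not randomised | Primary, basis of sample size |
| APP vs APP+PCA | 7 vs 7 | Randomised | Stated as not powered |

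Drawing the 7 comparison sites at random is random sampling. It makes them representative of their pool. It is not random allocation, because none of them could have been assigned an intervention.

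**2. What the safeguards cover.**
- Matching on sector and size, with attention to cultural make-up, balances those characteristics but not willingness.
- Within-clinic change removes fixed differences in level but not a difference in trend. The baseline for the testing rate is a single quarter, so the planned analysis contains no earlier trend to check. The sample size calculation assumes no change in control clinics.
- The reported absence of differences compares the two pools, not volunteers with others, and concerns volumes and intervals, not trends.
- The supplementary analyses of imbalance rely partly on asking clinic staff about confounders. Comparison sites are not contacted, so that information would be missing for them.

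**3. The two pools.** The counts add up: 89 + 297 = 386. The Inclusion Criteria list four conditions for intervention sites (county, at least 200 women, interval below 30 months, Quest laboratory). The list introduced by "For comparison, we will select from the following" repeats the same four. Nothing in the documents says what separates the 89 from the 297.

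**4. Illustration of size.** The documents give neither a volunteer effect nor a correlation between a clinic's rates before and after, so both are assumed here.
- From the plan: ICC 0.07, rate p = 0.50, m = 430 women per clinic, 7 clinics per group, 1% significance level (taken as two-sided).
- Assumed: no true effect, pre-post clinic correlation r of 0, 0.5 or 0.8, and a difference in trend b of 5 or 8 points.
- Variance of change per clinic: v = 2 × 0.07 × 0.25 × (1 − r) + 0.50/430, where 0.50 = 0.25 + 0.25 is the sampling part of the two quarters.
- SE of the difference: √(2v/7). Rejection probability: noncentral t, 12 degrees of freedom, noncentrality b/SE.

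| r | v | SE | False positives, b = 5 points | False positives, b = 8 points |
|---|---|---|---|---|
| 0 | 0.0362 | 0.102 | 1.7% | 3.0% |
| 0.5 | 0.0187 | 0.073 | 2.5% | 5.3% |
| 0.8 | 0.0082 | 0.048 | 4.7% | 12.8% |

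The bias in the estimate equals b whatever the value of r: 5/16 = 31% or 8/16 = 50% of the 16-point target.

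**5. Feasibility of three-way randomisation.** The plan's total reproduces: 3 × 7 × 430 = 9030, and it does not change. Willing sites needed rise from 14/89 = 16% to 21/89 = 24%. Group sizes stay the same, so the plan's power formula gives the same answer before and after the change.

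**The case against.** The strongest reply is that this is a disclosed choice with real merits. The protocol says openly that the comparison group is not randomised. Uncontacted sites also show usual care undisturbed by recruitment, which randomised controls would not. Matching, change scores, the reported similarity of the pools and a leave-one-clinic-out analysis are all in the plan. This stands as a reason to accept the comparison group when too few sites volunteer. It does not justify the trial label, and none of these measures addresses a difference in trend.

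Several stronger readings are tempting, but the documents do not support them.
- *The trial has no randomised evidence.* APP against APP+PCA is randomised and answers a stated question, the added benefit of educating women as well as providers (Choice of Comparators). It is not the primary contrast.
- *The comparison clinics are unwilling.* They are never asked. They are an unscreened mix, which may dilute a volunteer effect compared with setting volunteers against refusers.
- *The 89/297 split is itself a source of bias.* It is unexplained, but the protocol reports no differences between the pools on the listed variables. That willingness did not create the split is a reasonable inference from database counts and recruitment written in the future tense. No section states it.
- *The comparison places should be filled from the other 75 of the 89 sites (89 − 14).* If the letter and call go to those 89, as the wording suggests, the sites left after willing ones are removed are those that declined or did not respond. Using them would sharpen the contrast in willingness.
- *Surplus volunteers are the best comparators.* When more than 14 agree, the 14 are chosen for sector, size, geography and language. The surplus is therefore what deliberate selection leaves, and a comparison with it is still not randomised.

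**Conclusion.** The point holds in a limited form. Both primary contrasts are non-randomised comparisons of volunteer clinics with unscreened clinics. The reason given for this concerns data availability, not selection. A fall in testing relative to comparison could not be securely attributed to the app or tablet. That is weaker than saying the result would be uninformative or the intervention ineffective.

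The size of the bias is unknown from the documents. The figures above rest on assumed trends of 5 and 8 points and assumed correlations, and they show only that moderate trends matter against a 16-point target. The unexplained pool split is a gap in reporting, not a demonstrated bias. The change is worth making before enrolment because the plan already foresees more than 14 volunteers and already takes comparison outcomes from claims.

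**What to change.** 1. **At least 21 sites agree** (amend Overview and Study Enrollment Procedures). Select 21 willing clinics by the balancing factors already listed and randomise them three ways, 7 per group. The third group receives no further contact and is followed through claims.
2. **Fewer than 21 agree.** Keep the uncontacted, matched comparison sites. Do not fill places with sites that declined. Describe both intervention-versus-comparison results as non-randomised in the design label and in all conclusions, and reserve the word randomised for APP against APP+PCA. This applies equally when 15 to 20 sites agree.
3. **In either case,** state in the sample size section what separates the 89 sites from the 297.

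Cost: items 2 and 3 are wording only. Item 1 needs half as many willing clinics again (21/14 = 1.5), and the documents give no expected agreement rate, so it may not be reachable. It adds no site visits for the control group and no women to the total. Its small downside is that these controls will have had the recruitment letter and call, which might influence their practice.
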